#### Quality of Life Assessment:

The quality-of-life assessment will be conducted by two questionnaires from the European Organization for Research and Treatment of Cancer Quality of Life Questionnaire group, composed of the general questionnaire EORTC QLQ-C30 and its specific domain for TNE, the QLQ-GINET21, both available in Portuguese of Brazil by cross-cultural validation.

The QLQ – C30 general quality of life questionnaire was developed for cancer patients and is one of the most used in clinical cancer research, having already been applied by more than 80,000 cancer patients. Version 3 is the one currently used. It is

multidimensional, can be self-administered and consists of 30 questions that assess the patient in the last two weeks. The questionnaire addresses general questions about cancer, such as symptoms, side effects of treatment, psychological suffering, physical functioning, social interaction, sexuality, body image, global health, quality of life and satisfaction with medical care, regardless of the type of cancer. It is a generic quality of life document for cancer, composed of 30 questions that define the general quality of life, through five functional scales (physical, role/performance, cognitive, emotional and social), three symptom scales (fatigue, pain and nausea/vomiting) and six simple items (dyspnea, insomnia, loss of appetite, constipation, diarrhea and financial difficulties).

The scale in this questionnaire constitutes the following score: 1 (no), 2 (little), 3 (moderately), and 4 (a lot), except the global health scale. This consists of 2 questions that ask the individual to rate their general health and quality of life in the last week, through a score from 1 to 7, 1 being terrible and 7 being excellent. Scores are calculated separately for each of the scales (functional, QOL and symptoms), ranging from zero - 100. On the Global Health and functionality scale, the higher the score, the better the quality of life. In the symptom scales, the higher the score, the worse the score. In order to know the calculation in each scale, the average score in each of the scales is performed. After this average we make the linear transformation for the score to be 0-100, according to the formulas below:

- Gross score or Raw Score (RS): adds the score of each item and divides it by the number of items

- S score for functional scales:  $\{1 - (RS - 1) / \text{variation}\} \times 100$

- S score for symptom scale:  $\{(RS - 1) / \text{variation}\} \times 100$

- S-score for general health status / general quality of life:  $\{(RS - 1) / \text{variation}\} \times 100$

The variation is generally 3, since the items score from 1 to 4, except for the global health and quality scales that score a maximum of 7 and, therefore, there is a general variation of 6.

The complement of the QLQ-C30 for TNE, the QLQ-GINET21 questionnaire, is composed of 5 multi-item scales that address common symptoms in patients with NET, such as gastrointestinal and endocrine, concerns about illness, social role and symptoms of treatments; it also contains five items that assess weight loss/gain, bone/muscle pain,

sexual function. The methodology for calculating the scores is the same as that used by the questionnaire QLQ-C30.

Missing data often occurs in questionnaire studies. Researchers will try to minimize missing data by providing guidance to study participants. However, if it still occurs, several imputation methods can be used, and there is no standard method. The most common is to calculate the average of the scale of the answered items and use this average to input the missing value, provided that at least 50% of the items of that scale have been answered. This will be the method used in this study to treat possible missing data. When missing data occurs in single items, they should be excluded from the analysis.

The EORTC quality of life questionnaires will be applied at the baseline (within 4 days of treatment) and every 12 weeks (window of +/- 5 days) until the study leaves. The administration should preferably be on the day of the image, and always before the patient knows the result of the exam (so that the result does not influence the responses to the questionnaires) and by a trained investigator.

The total time to complete the QLG-C30 and LQL-GINET21 is approximately 20 to 30 minutes. The patient himself will complete the questionnaires; however, he may be helped by an investigator, if in doubt. In the end, it will be inserted in a closed envelope to ensure confidentiality and privacy.

### **Statistical plan**

Descriptive statistics will be used to report population characteristics, binary outcomes and adverse events. The Kaplan-Meier method will be used to report time-to-event variables and the reverse Kaplan-Meier method will be used to calculate the follow-up time for patients. For the analysis of quality of life, we will report the proportion of patients who increase the sum of the total score by at least 10% at 3 and 6 months after treatment - improvement of at least 10% is considered to be clinically significant by patients. We will also evaluate whether the global score varies and how much varies during the study for each patient; this analysis will be carried out in percentage and descriptively. The scores will be calculated according to the instruction manual of the EORTC group. The quality-of-life analysis will be carried out using the

intention to treat method, where patients who do not respond will be considered “non-responders” in terms of the effectiveness of the treatment.

Missing data in the questionnaires will be dealt with as described in the section above "Quality of Life Assessment".

The study sample will be 22 patients. For this calculation, we considered the 40-month disease control rate H0 to be 40% (placebo arm of phase III studies in TNE, such as the RADIANT417 study), H1 to 67%. Two-tailed type I error margin of 10%, power of 80% and loss of follow-up / non-adherence of 10% were considered.

We estimated a 40% screening failure (40% positivity on MIBG-I131).

All analyzes will be by intention to treat. Patients who receive at least one dose of MIBGI131 will be evaluated for toxicity and efficacy.

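### The quality-of-life responder rule counts a 10% increase in an undefined total with no stated direction, so equal-point improvement can go uncounted and symptom worsening can count as response

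*Combined protocol and SAP*

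**What the plan says.** The Statistical plan defines the quality-of-life result this way: "we will report the proportion of patients who increase the sum of the total score by at least 10% at 3 and 6 months". It justifies the threshold by adding that "improvement of at least 10% is considered to be clinically significant by patients", and on scoring it says "The scores will be calculated according to the instruction manual of the EORTC group".

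The Quality of Life Assessment section gives the scoring. For the QLQ-C30, "Scores are calculated separately for each of the scales (functional, QOL and symptoms"), each running from 0 to 100. The directions differ: "On the Global Health and functionality scale, the higher the score, the better the quality of life", whereas "In the symptom scales, the higher the score, the worse the score". No total is defined for either questionnaire, and no step reverses the symptom scores. The QLQ-GINET21 is said to be scored by the same method, without saying which formula applies to which of its scales.

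Secondary outcome 5 (Outcomes, Secondary) asks for an improvement of at least 10% in the baseline score on both questionnaires. The primary outcome (Outcomes, Primary) and secondary outcome 1 ask patients with functioning syndrome for a 10% improvement on the QLQ-GINET21. None of these passages names the score or its direction.

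**The concern.** A responder rule needs a defined quantity and a sign. This one counts increases in a sum whose components point in opposite directions. If it is programmed as written, some patients who get better are not counted and some who get worse are. If the analyst follows the evident intent instead, the total and its sign have to be chosen after data are available, because the plan does not fix them.

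At stake is the responder proportion at 3 and 6 months. With 22 patients, each misclassified patient moves that proportion by 1/22 = 4.5 percentage points.

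**Working it through.** The plan states no numerical result for this outcome, so there is no figure to reproduce. The check is algebra on the scale counts, then numbers at assumed baselines.

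**Inputs from the Quality of Life Assessment section.** The QLQ-C30 has five functional scales and one global scale (6 scores, higher is better), and three symptom scales and six single items (9 scores, higher is worse). The QLQ-GINET21 has five multi-item scales and five items (10 scores).

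**Assumed.** The documents give no baseline scores. I use three profiles of functional/global/symptom scores (F/G/S), with S the average of the nine: 90/80/10, 70/60/30 and 50/40/50.

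**1. Unreversed QLQ-C30 sum.** T = 5F + G + 9S.
- 450 + 80 + 90 = 620
- 350 + 60 + 270 = 680
- 250 + 40 + 450 = 740

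Best possible health gives 600 and worst possible health gives 900.

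**2. Every score better by d points.** Change in T = 6d − 9d = −3d, at any baseline. It is always negative, so it cannot reach +10%.

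**3. Changes at the assumed baselines.**

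| Change | Formula | T = 620 | T = 680 | T = 740 |
|---|---|---|---|---|
| All 15 scores 10 points better | −30/T | −4.8% | −4.4% | −4.1% |
| Points worse on each of the nine symptom scores that give +10% | 0.1T/9 | 6.9 | 7.6 | 8.2 |
| Points worse on all 15 scores that give +10% | 0.1T/3 | 20.7 | 22.7 | 24.7 |
| Average points better on the six functional/global scores alone that give +10% | 0.1T/6 | 10.3 | 11.3 | 12.3 |

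In the last row the rule works as intended. At 90/80/10 the figure of 10.3 is possible only as an average: the functional scores can gain at most 10 each, so the global score must gain more (5 × 10 + 12 = 62).

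**4. Single items.** By the symptom formula, one category on a single item is (1/3) × 100 = 33.3 points.
- Two such items one category worse: 66.7/T = +10.8%, +9.8%, +9.0%. This triggers the rule at the first baseline.
- Three such items: 100/T = +16.1%, +14.7%, +13.5%. This triggers it at all three.

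**5. Equal-percentage improvement.** The −3d result is for equal points.
- At 80/70/15, T = 605. A 20% relative improvement gives 5 × 96 + 84 + 9 × 12 = 672, or +11.1%, which counts.
- At 50/50/50, T = 750. The same 20% gives 300 + 60 + 360 = 720, or −4.0%, which does not.

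**6. Total read as the raw item sum.** Items are scored "1 (no), 2 (little), 3 (moderately), and 4 (a lot), except the global health scale". Of the latter the protocol says "This consists of 2 questions that ask the individual to rate their general health and quality of life in the last week", each rated 1 to 7. The functional formula falls as the raw score rises and the symptom formula rises towards worse, so 30 − 2 = 28 items are worse when higher. With an assumed item mean of 1.5, 2 or 2.5 and global items at 6, 5 or 4, the sums are 28 × 1.5 + 12 = 54, 28 × 2 + 10 = 66 and 28 × 2.5 + 8 = 78. Six, seven or eight items one category worse give 6/54 = +11.1%, 7/66 = +10.6% and 8/78 = +10.3%, each counted as improvement.

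**7. QLQ-GINET21.** If m of the 10 scores are symptom-type, equal-point improvement changes an unreversed sum by (10 − m)d − md = (10 − 2m)d. This is negative only if m is 6 or more, and the documents do not give m.

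**The case against.** The best defence is that the intent is clear. The Statistical plan glosses its own rule as improvement, the Outcomes section uses the same idea, and the directions of the scales are set out. An analyst would have to add opposing scales against the protocol's own description to get the wrong answer. This stands as evidence of intent, but intent supplies neither the total nor the sign. The EORTC manual is not among the documents, and the scoring that the protocol itself sets out is scale by scale, with no sum.

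A second defence is that the total means the two-question global health scale, for which an increase is the right direction. The next sentence of the Statistical plan does mention a global score. That sentence, however, introduces it as something to be evaluated in addition, and the protocol describes no global scale for the QLQ-GINET21. The reading cannot be excluded, but the text does not favour it.

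Two stronger readings are tempting and are not supported:
- **The rule is wholly inverted, or no uniform improvement can ever count.** Steps 3 and 5 show otherwise. Gains on functional and global scores alone can count, as can equal-percentage improvement at some baselines.
- **The sign error carries into the primary endpoint.** The primary outcome speaks of patients having improved, not of an increase. Only the lack of a defined QLQ-GINET21 score reaches it, and only for patients with functioning syndrome, whose share is not given.

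It is also fair that secondary outcome 5 is descriptive, with no test or decision attached.

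**Conclusion.** The concern holds in limited form. This is more than a missing detail: both QLQ-C30 sums that can be built from the documents, of scale scores or of raw items, misclassify some patients under the rule as written.

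The −3d result needs only the protocol's scale counts and directions, and applies to equal-point change. The percentages and point thresholds rest on assumed baselines and item means, shown as ranges. For the QLQ-GINET21 the size and even the presence of inversion depend on m, which is unknown.

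The consequence is confined to descriptive secondary outcome 5, plus an undefined score in the functioning-syndrome condition of the primary outcome and secondary outcome 1. It should be corrected, but it does not by itself undermine the radiological disease-control result.

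**What to change.** In the Statistical plan, replace the increase in the summed total with a signed definition, given separately for the QLQ-C30 and the QLQ-GINET21, by one of two routes:
1. a total in which symptom-type scores are first reversed (100 − S); or
2. one or more named scales with the direction of improvement stated: increase for global and functional scales, decrease for symptom scales.

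Also state:
- which scoring formula applies to each QLQ-GINET21 scale;
- whether 10% is relative to baseline or means 10 points on the 0–100 scale;
- how a baseline of zero is handled if it is relative;
- whether response is judged on each questionnaire separately.

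Use the same QLQ-GINET21 definition in the primary outcome and in the secondary outcomes that use it.

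Check of route 1: the reversed total 5F + G + 9(100 − S) is 1340, 1040 and 740 at the three assumed baselines. Ten points better on all 15 scores then gives 150/1340 = +11.2%, 150/1040 = +14.4% and 150/740 = +20.3%, all counted.

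Cost: questionnaires and visits do not change. The sponsor must commit to a score before seeing outcome data, and the responder proportion may change. Because the QLQ-GINET21 definition also enters the primary outcome for functioning syndrome, that part is not purely cosmetic. A relative 10% on a reversed total also leaves little room for patients with few symptoms: at 90/80/10 the largest possible gain is (1500 − 1340)/1340 = 11.9%.

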## **Hypotheses**

Well-differentiated NETs, with positive expression in the MIBG-I scintigraphy exam, will obtain significant radiological, symptomatic and biochemical control, and improved quality of life with therapeutic MIBG-I, which may be a treatment option instead of expensive, toxic and ineffective treatments, such as chemotherapy regimens, interferon alpha and/or liver debulking surgery.

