### **Secondary:**

1- Disease control rate (DCR). Defined by absence of radiological progression in conventional imaging examinations by RECIST 1.1 at 3 months after the end of treatment. For patients with functioning syndrome, beside radiological DCR, patients should have improved in at least 10% of the baseline score of quality-of-life (EORTC QLQ-GINET21) and stability or decrease in tumor markers.

2- Progression-free survival. Defined by time from day 1 cycle 1 to death from any cause or radiological progression by RECIST 1.1, whichever occurs first. Patients alive and without progression at the time of study analysis will be censored for time-to-event analysis.

3- Radiological response rate. Assessed by RECIST 1.1 criteria.

4- Rate of Biochemical response. Defined by at least 30 percent drop in the tumor marker (24-hour urine 5-hydroxyindoleacetic acid (5-HIAA) and/or specific hormone), if functioning syndrome, at any time of treatment in relation to pre-treatment value.

5- Quality of life. Assessed by the EORTC QLQ-C30 and QLQ-GINET21; both available in Brazilian Portuguese. Improvement of at least 10% in the baseline score at 3 and 6 months after the end of the treatment will be considered clinically meaningful. Improvement by 10% of the baseline score at 3 and 6 months will be considered clinically meaningful.

6- Incidence of Treatment-related Adverse Events. Frequency of adverse events of grades 2 or more by Common Adverse Event Toxicity Criteria (CTCAE) version 5.0.

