## **Methodology**

### **Study design**

This is a single-arm, unicentric, single-stage, phase 2 clinical study of therapeutic metaiodobenzylguanidine (MIBG) for patients with metastatic well-differentiated neuroendocrine tumors and radiological progression or intolerance after standard lines of treatment and with MIBG-I positive scan.

Eligible patients will receive MIBG-I in up to 4 doses of 7,400Mbq (200 mCi) each, with an interval of at least 60 days. The administration of the cycles will depend on the results of the haematological exams, therefore, each patient will be able to receive from 1 to 4 cycles; In the experience of A.C.Camargo Cancer Center, most patients receive between 3 and 4 cycles. MIBG-I is administered intravenously to an inpatient, being discharged when reaching limits of radiological exposure recommended by the National Nuclear Energy Commission (invariably, 24 hours). The dose of 200mCi

per application for up to 4 doses of MIBG-I used in this protocol is the same used in routine at the institution and is also used in other PPRT treatments. This dose is safe and practiced by the service for at least a decade.

Clinical and toxicity assessments will take place every 2 weeks with medical history, physical examination and general laboratory until resolution of toxicities (usually 30 days after treatment). Imaging exams (chest, abdomen and pelvis CT scans) and 5-HIAA dosage in 24-hour urine (functioning tumors) will be performed at the beginning of treatment, and every 3 months until progression or exit from the study. Symptom assessment will be conducted using quality of life questionnaires that will be administered before treatment and every 3 months until progression. Toxicities will be measured in all medical visits through CTCAE version 5.0. Consultations, laboratory and imaging tests are already part of the treatment routine of these patients. The extra routine interventions, that is, the study, are the MIBG-I scintigraphy exam, the treatment with MIBG-I and the quality-of-life assessments.

Clinical data will be prospectively collected in an electronic database (REDCap) and will include sex, age, primary tumor site, performance scale status, functionality, metastatic disease duration, metastasis sites, degree of liver impairment, comorbidities, previous treatments, scores of quality of life results and toxicity.

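### Quality of life is summarised only as the share improving by at least 10% and as per-patient percentages; a single-arm trial has no reference for that share, and no change in points with an interval is planned

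*Combined protocol and SAP*

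**What the plan says.** Two summaries are planned in the Statistical plan. The first: "we will report the proportion of patients who increase the sum of the total score by at least 10% at 3 and 6 months", counted from the end of treatment. The second looks at how far each patient's global score varies during the study, and "this analysis will be carried out in percentage and descriptively". Outcomes, Secondary, item 5 ties the cut to the patient's own starting value: "Improvement of at least 10% in the baseline score at 3 and 6 months after the end of the treatment" counts as clinically meaningful. The Statistical plan supports the 10% by a citation on what patients perceive as meaningful. It also counts patients who do not respond as non-responders.

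The data collected are richer than these summaries. According to the Quality of Life Assessment section, "Scores are calculated separately for each of the scales (functional, QOL and symptoms), ranging from zero - 100", and the questionnaires are given at baseline and every 12 weeks. The general sentence on descriptive statistics covers population characteristics, binary outcomes and adverse events, so it does not supply a group summary of the scores.

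The design has no comparator: "This is a single-arm, unicentric, single-stage, phase 2 clinical study". The Hypotheses section nevertheless expects "improved quality of life with therapeutic MIBG".

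**The concern.** A share of improvers can be read only against the share expected if nothing changes. A randomised trial gets that from its control arm; this trial has none, and the plan names no external reference rate. Nor does it report the mirror-image share worsening by at least 10%, which would show a reader how much of the improver share is plain variation.

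Expressing change as a percentage of a variable baseline adds a second difficulty. A patient who happens to start low and rebounds shows a large positive percentage, while a patient who starts high and falls back shows a smaller negative one. Averaged, such percentages come out above zero with no true change. A baseline of 0 has no percentage at all.

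Improved quality of life is one of the trial's hypotheses, and the section on global innovation potential presents its assessment as a first for this treatment. Followed as written, the plan could report a sizeable group with clinically meaningful improvement, and the reader could not tell how much of it is noise.

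**Working it through.** **The plan's own figure.** No quality-of-life mean, SD, correlation or sample size is given. The only sample size is for disease control, with 40% against 67%, two-sided 10% and power 80%: n = [(1.645·√0.24 + 0.842·√0.2211) / 0.27]² = (0.806 + 0.396)² / 0.0729 = 19.8, so 20, and 20 × 1.1 = 22. The 22 patients therefore reproduce, and they were not sized on quality of life.

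**Assumed inputs.**
- *Global scale:* two items, each answered "through a score from 1 to 7, 1 being terrible and 7 being excellent", give 13 levels in steps of 100/12 = 8.33 points. Assumed mean 60, SD 20, SD of change 15, 20 or 25. An SD of change of 25 implies a correlation of 1 − 625/800 = 0.22, so it is an extreme case.
- *Finer summed score:* treated as continuous, assumed mean 60-80, SD 12-15, SD of change 8-12.

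**Chance share, global scale.** One step is at least 10% of any baseline up to 83.3 (8.33/83.3 = 0.10). Below that, the smallest possible rise counts as an improvement. Simulated with no true change, scores rounded to the steps and clipped to 0-100:

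| SD of change | Improve ≥10% | Worsen ≥10% | Mean % change | Median % change |
|---|---|---|---|---|
| 15 | 38% | 37% | +5% | 0 |
| 20 | 41% | 40% | +9% | 0 |
| 25 | 43% | about 42% | +13% | 0 |

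Varying the mean over 50-70, the SD over 20-25 and the correlation over 0.4-0.8 gives 34-42%. Together, that is roughly 35-43%.

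**Chance share, finer summed score.** Let m be the mean, s the SD and d the SD of change. A patient improves if follow-up − 1.1 × baseline ≥ 0. With no true change this quantity has mean −0.1m and variance 1.1d² + 0.01s².
- m = 60, s = 12, d = 12: variance 158.4 + 1.44 = 159.84, z = 6/12.64 = 0.475, share 32%.
- m = 60, s = 15, d = 10: variance 110 + 2.25 = 112.25, z = 6/10.59 = 0.566, share 29%.
- m = 80, s = 12, d = 8: variance 70.4 + 1.44 = 71.84, z = 8/8.48 = 0.944, share 17% (about 16% with the ceiling at 100).

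So 16-32% on these inputs. A wider grid (SD 15-25, mean 50-70, correlation 0.5-0.9) gives 16-40%, and SD 10 with mean 50-80 gives 5-32%. About 15-35% is a fair central range.

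**Non-responder rule.** If the plan's 10% loss is all missing questionnaires, multiply by 0.9: the global-scale figures of 38%, 41% and 43% become 34%, 37% and 39%, and 16-32% becomes 14-29%. With an assumed 30% missing, the global-scale figures fall to 27%, 29% and 30%.

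**Drift of an averaged percentage.** To first order it is d²/(2m²): 64/12,800 = +0.5% at m = 80, d = 8, and 144/7,200 = +2.0% at m = 60, d = 12. Simulation gives +0.5% to +2.6% for the finer score and, because low baselines weigh heavily, +5% to +13% for the global scale at mean 60. The mean change in points stays at about 0 throughout.

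**Precision at n = 22.** For 9 improvers (41%), the exact 90% interval is 23% to 60%, a half-width of (60 − 23)/2 = 18.5 percentage points. For the mean change, the 90% half-width is 1.721 × SD/√22: 5.5 points at SD of change 15, 7.3 at 20 and 9.2 at 25. The two are in different units, but both run over a 0-100 range.

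**The case against.** Reporting a prespecified secondary outcome descriptively in a 22-patient phase 2 trial is defensible, and the 10% cut has a cited basis in what patients notice. That stands, and it is a reason to keep the share. It does not explain why the full-scale change is left out.

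Three stronger readings are tempting and should be resisted.

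- *About 40% improve by chance.* That figure belongs to the two-item global scale under assumed values. The 10% cut in the Statistical plan applies to the summed total score, which is probably finer and gives a lower share. The non-responder rule lowers it again.
- *The cut costs power.* No quality-of-life test is planned, so there is no planned power to lose. A comparison would need an invented test against a chance share that the trial cannot know.
- *The planned percentages are biased upward.* The drift arises only if they are averaged. The plan describes each patient and names no average, and the median stays near 0.

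A further objection stands in part: a mean change in points does not replace a control arm. Zero is its natural reference only without regression to the mean, open-label expectation or selective dropout. Study design stops questionnaires at progression, while the Quality of Life Assessment section continues them until the patient leaves the study. Either way, later scores come mainly from patients doing better. Replacing the non-responder analysis by a model that assumes data missing at random would therefore be hard to defend.

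**Conclusion.** The point holds as a cheap improvement to a secondary outcome. The plan limits quality of life to an improver share without an internal reference and to descriptive per-patient percentages, although it collects 0-100 scores repeatedly. With no true change, a substantial share would pass +10%: roughly 35-43% on the global scale and about 15-35% on a finer summed score, and less after counting missing patients as non-responders. All of these rest on assumed means, SDs and correlations; none is a figure from the documents. An averaged percentage would drift by about +0.5% to +13%.

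What is lost in practice is precision and interpretability. At n = 22 an improver share is known only to within about 18 percentage points either way, while the same patients would give a mean change to within about 5.5 to 9 points. The documents do not support saying that the trial will report a false improvement, or that it is underpowered for quality of life.

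**What to change.** In Outcomes, Secondary, item 5 and in the Statistical plan, keep the prespecified share improving by at least 10%, with its non-responder rule, and add beside it:

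1. The mean change from baseline in points (0-100) at 3 and 6 months after treatment with a 90% CI for the QLQ-C30 global score, and descriptively for each GINET21 scale. A paired t interval is enough; a baseline-adjusted model is an alternative.
2. Each patient's change in points in place of the percentage of baseline.
3. The share worsening by at least 10%, next to the share improving. State the direction for each scale, since "In the symptom scales, the higher the score, the worse the score".

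State the number of patients contributing at each time. Say plainly that the change in points describes patients still being assessed and may be optimistic, which is why the non-responder analysis stays alongside.

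The cost is a few lines of text and a little analysis. No new data, visits or patients are needed.

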## **Outcomes**

### **Primary:**

Disease control rate (DCR). Defined by absence of radiological progression in conventional imaging examinations by RECIST 1.1 at 6 months after the end of treatment. For patients with functioning syndrome, beside radiological DCR, patients should have improved in at least 10% of the baseline score of quality-of-life (EORTC QLQ-GINET21) and stability or decrease in tumor markers.

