#### Effectiveness and Follow-up Assessments:

For evaluation of efficacy, patients will undergo imaging tests (chest, abdomen and pelvis tomography or abdomen and pelvis resonance) at baseline (within 8 weeks of starting treatment) and every 12 weeks (+/- 5 days) until progression or withdrawal from the study. Patients will also be evaluated for signs and symptoms that may be related to disease progression. Patients who present clinical progression, according to the investigator's judgment, but without radiological progression, will be able to discontinue the treatment and continue the image evaluation until progression; however, if new treatment is instituted, the last date of receipt of MIBG-I will be the censorship date in the progression-free survival analysis.

After documenting progression or leaving the study for other reasons, patients will be followed up by the investigator or another oncologist from the Clinical Oncology team for symptom control, image monitoring and possible future therapies. The patient continues to be cared for at the A.C.Camargo Cancer Center, if desired.

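### If 67% applies to assessed patients, losing 2 of 22 leaves exact power of 67.3% rather than the stated 80%, and the primary DCR has no named test, cut-off or missing-scan rule

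*Combined protocol and SAP*

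**What the plan says.** The Statistical plan gives 22 patients, a null DCR of 40%, an alternative of 67%, and: "Two-tailed type I error margin of 10%, power of 80% and loss of follow-up / non-adherence of 10% were considered". The Abstract gives the same figures. It calls the 40% a 6-month rate, where the Statistical plan calls it a 40-month rate; I use 6 months, and the arithmetic is the same either way.

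On analysis, the Statistical plan says: "Descriptive statistics will be used to report population characteristics, binary outcomes and adverse events". On the analysis set: "All analyzes will be by intention to treat. Patients who receive at least one dose of MIBGI131 will be evaluated for toxicity and efficacy". No test, critical count or interval rule is given for DCR, although the Abstract and the sections on innovation and cost-effectiveness draw consequences from a positive study.

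The primary outcome is "Defined by absence of radiological progression in conventional imaging examinations by RECIST 1.1 at 6 months after the end of treatment". In functioning syndrome, in addition, "patients should have improved in at least 10% of the baseline score of quality-of-life (EORTC QLQ-GINET21) and stability or decrease in tumor markers".

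The nearby rules for incomplete data are each written for something else:
- The Statistical plan's intention-to-treat sentence, "where patients who do not respond will be considered" non-responders as to treatment effectiveness, has the quality-of-life analysis as its subject.
- The item rule under Quality of Life Assessment ("When missing data occurs in single items, they should be excluded from the analysis") covers questionnaires.
- The censoring rule under Effectiveness and Follow-up Assessments covers progression-free survival.

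**The concern.** The sample size makes a 10% allowance for losses, while the analysis section keeps every dosed patient. If the allowance was made by taking lost patients out of the denominator, the analysis that is actually described may not deliver the stated power. With no test or cut-off written down, the verdict in a borderline result, and whether 80% power was ever available, would depend on choices that could still be made once the results are known.

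**Working it through.** **Inputs.** p0 = 0.40, p1 = 0.67, two-sided level 10%, power 80%, loss 10%, n = 22 (Statistical plan). Two of 22 is 9.1%, the nearest whole number to 10%.

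**1. The plan's own figure.** One-sample normal approximation: n = [1.645·√(0.4·0.6) + 0.842·√(0.67·0.33)]² / 0.27² = 19.80, and 19.80/0.9 = 22.0. Approximate power with 20 assessed is 80.4%. So 22 is reproduced. The plan shows no formula; that 67% is meant for about 20 assessed patients is inferred from this match.

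**2. Exact error rates under 40%.**
- n = 22: P(X≥13) = 0.0551, P(X≤4) = 0.0266. The minimum-likelihood test rejects at X≤4 or X≥13, size 0.0817. With at most 5% per tail the cut-off is 14, P(X≥14) = 0.0215.
- n = 20: P(X≥12) = 0.0565, P(X≤4) = 0.0510. The z-test rejects at X≤4 or X≥12, size 0.1075, above 10%. Both exact conventions need 13, P(X≥13) = 0.0210.

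**3. Power at 67%** (assumption where 2 are lost: loss is independent of outcome, and 67% applies to the 20 assessed).

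| Situation | Rule | Power |
|---|---|---|
| All 22 assessed, or 67% net of losses | ≥13/22 (minimum-likelihood or z) | 84.5% |
| Same | ≥14/22 (at most 5% per tail) | 71.9% |
| 2 lost, excluded | ≥13/20 (either exact convention) | 67.3% |
| 2 lost, kept as not controlled | ≥13/22 (minimum-likelihood or z) | 67.3% |
| 2 lost, kept as not controlled | ≥14/22 (at most 5% per tail) | 49.2% |
| 2 lost, excluded | ≥12/20 (z-test, size 10.7%) | 81.8% |

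The two 67.3% rows are the same probability, P(X≥13 | 20, 0.67). If instead each dosed patient has a 10% chance of being lost and counted as not controlled, the rate is 0.67 × 0.9 = 0.603 and P(X≥13 | 22, 0.603) = 63.5%.

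**4. The borderline result 13/22.** z-test p = 0.068 and minimum-likelihood exact p = 0.082: positive. Doubled exact tail p = 0.110 and 90% Clopper-Pearson interval 39.5% to 76.7%: negative. If the true rate is 67%, exactly 13/22 has a 12.7% chance of occurring.

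**5. Effect of the missing-component rule on the verdict.**
- 12 controlled, 2 lost: 12/20 gives z p = 0.068 and minimum-likelihood p = 0.107; 12/22 gives 0.164 and 0.193. The verdict turns under the z-test only.
- 12 controlled, 3 lost: 12/19 gives 0.039 and 0.058. Against 12/22 the verdict turns under both.
- By the doubled tail, 13 controlled with 2 lost also turns: 13/20 has p = 0.042 and 13/22 has p = 0.110.

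**6. Which scan.** Under Effectiveness and Follow-up Assessments, imaging is "every 12 weeks (+/- 5 days) until progression or withdrawal from the study". Table 2 allows doses at day 1 and weeks 8, 16 and 24. Six months (24 to 26 weeks) after a last dose at week 8 or 16 is week 32–34 or 40–42, while 12-weekly scans fall at weeks 24, 36 and 48. Table 2's follow-up column, marked for CT, allows 12- or 8-weekly visits; 8-weekly visits after week 24 would fall at weeks 32 and 40. The two places do not settle which scan decides the primary outcome.

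**The case against.** The plan's apparent method does deliver what it states: about 20 assessed patients give about 80% by the normal formula, and the loss is already in the 22. The 67.3% applies a different test. Under the minimum-likelihood test the fall does not come from the missing-data gap, because the cut-off is 13 for 20, 21 and 22 patients; it comes from the discreteness of the binomial and from 67% being before losses. All of this stands, and it limits what can be claimed. It does not rescue the 80%. The z-test reaches 81.8% only by removing the 2 patients and exceeding the stated 10%. If they were dosed and are kept, as the plan's analysis set implies, the z-test also needs 13/22 and has 67.3%.

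It is also fair to say that the non-responders sentence speaks of treatment effectiveness, that the plan then declares intention to treat for all analyses, and that GINET21 is itself a DCR component. Extending the sentence to a missing questionnaire, and to DCR generally, is a natural reading. It is not written, and no rule names the scan or the marker.

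Finally, 14/22 is as defensible as 13/22. The plan needs to choose one; this review does not require the more favourable choice.

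**Conclusion.** The concern holds, conditionally. If 67% applies to assessed patients and 2 of 22 are lost independently of outcome, the usual exact tests at two-sided 10% have 67.3% power (49.2% with at most 5% per tail and the losses kept as not controlled), against a stated 80%. If all 22 are assessed, or 67% is net of losses, power is 84.5% at ≥13/22 and 71.9% at ≥14/22. Separately, no rule defines a positive study, and 13/22 changes verdict with the convention.

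A reader might infer three stronger things that the documents do not support:
- That 22 is a calculation error. It reproduces.
- That the plan has no missing-data handling. It has rules for quality of life and progression-free survival; the gap is the scan, the marker, and whether the non-responders sentence carries over to DCR.
- That the missing-data gap causes the drop to 67.3%. Under the minimum-likelihood test, excluding or keeping the 2 gives the same power.

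**What to change.** Before outcome data are seen, amend the Statistical plan:

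1. **Power.** Say whether 67% is before or after losses, and replace the 80% with, for example: exact power 85% if all 22 are assessed (≥13/22, minimum-likelihood test); 67% if 2 of 22 are lost and 67% applies to assessed patients.
2. **Decision rule.** Name one test, its two-sided convention and its critical count for the number dosed: for example ≥13/22 by the minimum-likelihood exact test, or ≥14/22 with at most 5% per tail and its lower power stated. Report a confidence interval built on the same convention. A Clopper-Pearson interval beside a 13/22 rule would contradict the verdict at 13/22.
3. **Missing components.** State that a dosed patient lacking the 6-month scan or, in functioning syndrome, the marker or GINET21 score counts as not controlled. Add a sensitivity analysis in patients with a complete assessment.
4. **Timing.** State which scheduled scan is the 6-month one, and reconcile the 12-weekly schedule with Table 2.

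The cost is wording only, and a less favourable stated power. Enlarging the trial is not proposed. At 60.3%, 80% power is first reached at 35 patients by the minimum-likelihood exact test and holds at every larger size checked (to 89) only from 40; the normal formula gives 36. The screening yield is itself inconsistent: 50% positivity in the Abstract, and 40% positivity beside 40% screening failure (which implies 60%) in the Statistical plan. At 60% to 40%, 35 to 40 patients would mean screening 35/0.60 ≈ 59 to 40/0.40 = 100, against 2 × 35–40 = 70–80 metastatic patients treated at the centre over the 2 recruitment years (Study time), before eligibility is applied.
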